Study Aims:	
 1. To conduct a proof-of-concept, mechanistically-driven, double-blinded, placebo-controlled trial, to examine effects of GKT137831 administration on a surrogate measure of oxidative stress and pulmonary injury in IPF patients. 2. To determine effects of GKT137831 administration in IPF patients, compared to placebo, on four secondary efficacy endpoints: (a) levels of collagen degradation product, C1M, measured in sera by ELISA; (b) and forced vital capacity (FVC) at baseline and 24 weeks. Also (c) six-minute walk distances (6MWD) will be measured at baseline and 24 weeks; and (d) adverse events (AE) will be recorded throughout the subject's participation in this study.

Study Design:	
Following screening assessments, IPF patients who meet all inclusion/exclusion criteria will be randomly assigned to receive one of the following treatments in a ratio of 1:1:
 
 • Arm A (n=30) – GKT137831 Treatment: GKT137831 will be administered orally, at a dose of 400 mg bid, for a total of 24 weeks. • Arm B (n=30) - Placebo Treatment: Arm B subjects will receive matching placebo for the same duration. 
Participants will be followed in face-to-face visits with trial personnel every 6 weeks for 24 weeks to assess drug effects and monitor safety during their treatments, and by phone surveillances one month thereafter.

Planned Sample Size:	A total of 60 subjects will be enrolled in this multi-center trial from among IPF patients at 5 participating medical centers.
Duration of Study:	Up to a maximum of 32 weeks, including screening (4 weeks maximum), drug administration for 24 weeks, and then a final surveillance phone contact 4 weeks later.
Inclusion Criteria:	
 1) Age between 40-85 years old. 2) A diagnosis of IPF that fulfills current ATS/ERS Consensus Criteria (1). 3) IPF duration <10 years, based on the date of definitive diagnosis. 4) Ability and willingness to give informed consent and adhere to study requirements. 5) Ratio of forced expiratory volume in 1 second to forced vital capacity (FEV₁/FVC) >70% of predicted values

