1.2 SPECIFIC AIMS

Central Hypothesis: Our primary hypothesis is that treatment of IPF patients with the NOX1/4 inhibitor GKT137831 will reduce pulmonary oxidative injury, as ascertained by reductions in plasma levels of a mechanistic surrogate biomarker (*o,o'*-dityrosine). A corollary of this hypothesis is that treatments that reduce oxidative injury in these patients will have a favorable effect on the natural history of IPF.

The studies proposed here are primarily designed to determine the magnitude of the ROS metabolite reduction and further assess safety of GKT137831 in IPF patients. Nonetheless, we hope that experimental treatments may result in clinically-relevant beneficial effects, as determined by secondary endpoints that include preservation of forced vital capacities and ability to ambulate.

The Specific Aims of this Trial are:

1. To conduct a double-blinded, placebo-controlled Phase II clinical trial in 60 ambulatory IPF subjects at five major medical centers. Subjects will be randomized 1:1 to GKT137831 or matching placebo, and treated for six months. The primary endpoint of this trial will be treatment effects of the experimental drug on plasma levels of *o,o'*-dityrosine, measured by mass spectroscopy pretreatment and at six-week intervals.

*We hypothesize the experimental therapy will reduce plasma levels of *o,o'*-dityrosine, reflecting target engagement of the drug, and reductions of oxidative stress and injury.*

2. To determine the efficacy of GKT137831 therapy in IPF patients, compared to placebo, on four secondary endpoints, measured at baseline and at six-week intervals of: (a) collagen degradation product, C1M, measured in sera by ELISA; and (b) FVC; (c) and 6MWD at baseline and 24 weeks week intervals.

We hypothesize the experimental therapy will decrease circulating levels of C1M. Although the short-duration treatment in this Phase II clinical trial may not result in significant effects on the secondary clinical endpoints, the results of these studies will be critical for the design and power analyses of future GKT137831 Phase III trials. Moreover, this as-of-yet untested drug treatment for IPF may prove to be very effective, and these measures will enable us to detect an unprecedented benefit of this novel approach.

3. To assess the safety and tolerability of GKT137831 in patients with IPF. The incidence and severity of AEs, laboratory tests and ECG abnormalities will be assessed over the course of the trial.

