2.7 STUDY ENDPOINTS

2.7.1 Primary Efficacy Endpoint:

The primary endpoint of this trial will be treatment effects of GKT137831 on plasma levels of *o,o'*-dityrosine, measured by mass spectroscopy pretreatment and at six-week intervals, in comparisons to effects of placebo alone.

O,o'-dityrosine is a mechanistic surrogate biomarker of oxidative stress. This metabolite is synthesized by myo-fibroblasts in fibroblastic foci, and is associated with cellular injury and ECM cross-linking (Secs. 1.3.5., and 1.3.6.). Levels of *o,o'-dityrosine* are increased in IPF patients (Sec. 1.3.7.) and were significantly decreased by GKT137831 administration in a murine model of fibrotic lung injury (Sec. 1.3.9.).

We hypothesize plasma levels of *o,o'*-dityrosine in IPF participants will be reduced by NOX inhibition with GKT137831, reflecting beneficial effects of the experimental drug on fibrosis (Sec. 1.3.8).

2.7.2. Secondary Efficacy End-Points:

Secondary endpoints are: (a) collagen degradation products (e.g.C1M), measured in sera by ELISA; (b) forced vital capacity (FVC); and (c) six-minute walk distance (6MWD) comparing baseline and values at 24 weeks; and (e) adverse events (AE) that occur anytime during the duration of the trial.

a) C1M: Circulating concentrations of collagen digest fragments (e.g., C1M) are reflective of ECM turnover, and increased levels discriminate IPF patients vs. controls, and are prognostic of disease activity and outcome (Sec. 1.3.10.). C1M will be measured by competitive ELISA in serum specimens collected by phlebotomy at visits that occur every 6 weeks in all patients. The assays will be performed at Nordic Biosciences (Herlev, Denmark), as previously described (16). We hypothesize GKT137831 treatment will result in decreased ECM turnover and reductions of sera C1M levels, in comparison to placebo effects.

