b) and c) FVC and 6MWD: This is a Phase IIb study and is likely underpowered for rigorous evaluation of drug effects on clinical endpoints, such as FVC changes and/or 6MWD over time. Nonetheless, measures and comparisons of these parameters will enable us to detect striking drug efficacy, and will likely be informative with respect to power calculations for later, more definitive efficacy trials. FVC is a measure of pulmonary restriction (in turn, a function of the underlying lung fibrosis). 6MWD are simple, inexpensive, reproducible measures of global cardiopulmonary function. Values for 6MWD can be obtained in all patients, even those who are immobile (e.g., value = 0). Measures of FVC and 6MWD will be performed per ATS/ERS guidelines. These tests are standard of practice (SOP) in our IPF clinics.

2.7.3. Safety Endpoints:

Adverse events: Adverse events (AE) that occur anytime during participation in this study will be recorded and compared. The NCI Common Toxicity Criteria Scale will be used to define grades (severity) of adverse events and toxicities. An AE is defined as any untoward medical occurrence in a subject, regardless of its relationship to these treatments. Toxicity is an adverse event with a direct relationship to the study drug. All toxicities are AE, but not all AE are toxicities. Computer data entry (and case report forms- [CRF]) will require responses to all adverse events, with a particular focus on infections (including location and organism), and metabolic perturbations (e.g., cardiac, liver, bone marrow, or thyroid abnormalities) hyperglycemia, hypotension, etc.). Recording all AEs in pre-specified checklists (and free text entries), will guard against unintended bias in this unblinded trial. We hypothesize GKT137831 will be safe in this population, and will not be associated with an increased number or severity of AE in comparison to placebo.

2.7.4. Pharmacokinetic endpoints:

Plasma concentrations of GKT137831 and its main phase 1 metabolite, GKT138184. The plasma concentrations will be subjected to population PK analysis to estimate population PK parameters such as clearance and volume of distribution and associated inter-individual variability (IIV), and to determine predictors of IIV. PK-PD analysis will be carried out using the primary endpoint and selected secondary endpoints in order to explore any potential PK- PD relationships.

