2.8 DATA ANALYSES AND POWER ANALYSES

2.8.1. Data analyses: Baseline demographic and clinical data of participants will be summarized using means (with standard deviations) and medians (with inter-quartile ranges) for continuous variables, and counts and percentages for discrete variables, stratified by treatment group. Differences between groups (to examine the randomization effectiveness), will be assessed by t-tests, or by Fisher's exact test for discrete data. Analyses will follow intention to treat principles, with the last observed outcome over all time points being used as the primary measure for a given variable. Multiple imputation will be used based on subject characteristics to assess the obvious issues, with last observations carried forward in these analyses. Trajectories over time, for a given patient and outcome measure, will be displayed via line graphs, and assessments conducted using generalized linear models on the repeated time points. Comparisons between the treatment arms of circulating o,o'-dityrosine levels at various time points will be made using these repeated measures techniques. Transformations of these tests may be needed, such as velocities, if many individuals are unable to complete the entire protocol.

2.8.2. Power analyses: The sample size of 60 for this clinical trial (equally divided between experimental and placebo arms) is based on exposing a minimum number of patients to risks of experimental therapy, while still obtaining useful information. We previously found that o,o'-dityrosine levels ($\mu\text{mol/mol}$ tyrosine) in IPF patients ($n = 32$) were 8.51, with a standard deviation (SD) of 5.30, compared to mean and SD of 0.47 ± 0.45 in normal controls (15). Assuming o,o'-dityrosine levels are reduced in the experimental arm subjects by 50% of the difference between untreated IPF and normals (e.g., to $4.02 \mu\text{mol/mol}$ tyrosine), with a SD of 5.3 we will be able to reject the null hypothesis that the population means of the experimental and control groups are equal with probability (power) 0.82, using an unpaired, two-way t-test. The Type I error probability associated with this test of this null hypothesis is 0.05. The 50% reduction is well within ranges in which ROS and fibrosis markers are decreased by GKT137831 in other models (Sec. 1.3.9., and 8-11).

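### Aim 2 still puts FVC on a six-week schedule that the visit plan does not have, and Section 2.8.1 names no baseline-adjusted Week 24 comparison for FVC or 6MWD

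*Combined protocol and SAP*

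**What the plan says.** **Timing of FVC.** Section 1.2, Aim 2, describes the secondary endpoints as "measured at baseline and at six-week intervals of: (a) collagen degradation product, C1M, measured in sera by ELISA; and (b) FVC". The synopsis version of the same aim reads "forced vital capacity (FVC) at baseline and 24 weeks". Section 2.2 places lung function tests before and after therapy. Section 2.6.3 lists one pre-treatment spirometry. Section 2.6.4 lists spirometry at Day 168 and at no other on-treatment visit, and Table 1 marks Weeks 0 and 24 only.

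**Timing of 6MWD.** Aim 2 says "6MWD at baseline and 24 weeks week intervals", which is garbled but is not six-weekly. The synopsis says "six-minute walk distances (6MWD) will be measured at baseline and 24 weeks" and Section 2.7.2 says "six-minute walk distance (6MWD) comparing baseline and values at 24 weeks". These agree with Table 1.

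**Analysis.** Section 2.8.1 gives one general plan. The last observed outcome is the primary measure for each variable, supported by multiple imputation. It adds "Trajectories over time, for a given patient and outcome measure, will be displayed via line graphs", with "assessments conducted using generalized linear models on the repeated time points", and mentions velocities as a possible transformation. The one between-arm comparison that it ties explicitly to repeated measures concerns o,o'-dityrosine. No model, contrast or covariate is given for FVC or 6MWD. Section 2.7.2 speaks of effects on clinical endpoints "such as FVC changes and/or 6MWD over time" and concedes that the trial is likely underpowered for them.

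**The concern.** Two passages of current text give different schedules for the same secondary endpoint. The amendment log explains how this arose (the Week 6, 12 and 18 lung function and walk tests were removed in Version 7.0), but the point does not depend on the log, because both readings stand in the present protocol.

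The analysis section has the same gap in a form that matters more. Trajectories, velocities and models over several visits suit o,o'-dityrosine and C1M, which are still sampled every six weeks. FVC and 6MWD have one value after baseline. For them the reader must work out which quantity is compared between arms and what part the baseline value plays. The choices differ greatly in precision, and the choice could be made after the data are seen. Section 1.2 says that these results will inform the design and power of later Phase III trials, so an imprecise estimate would carry forward.

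**Working it through.** **1. The plan's own power figure.** Section 2.8.2 supplies means of 8.51 and 0.47, SD 5.3, 30 per arm and two-sided alpha 0.05. The difference is 0.5 × (8.51 − 0.47) = 4.02. The standard error is 5.3 × √(2/30) = 1.368, so the noncentrality is 4.02 / 1.368 = 2.94. The two-sample t-test then has power 0.823, which reproduces the stated 0.82. It concerns o,o'-dityrosine and does not change here. The plan states no power for FVC or 6MWD.

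**2. Measurements per patient.**

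| Endpoint | Section 1.2, Aim 2 | Visit list and Table 1 |
|---|---|---|
| C1M | baseline, Weeks 6, 12, 18, 24 | blood drawn at the same five times |
| FVC | baseline, Weeks 6, 12, 18, 24 (as worded) | baseline, Week 24 |
| 6MWD | baseline, Week 24 | baseline, Week 24 |

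Only the FVC row conflicts.

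**3. Can a repeated-measures model be fitted to two points?** Yes. On simulated data with 30 per arm, the arm-by-time term of a mixed model was 0.3324 (SE 0.1209). A t-test on change gave 0.3324 (SE 0.1209). The two are the same comparison.

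**4. What the unstated choice costs.** Let r be the correlation between baseline and Week 24, with equal SD at both times and 30 per arm. The standard errors of the arm difference are:

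- last value, unadjusted: SD × √(2/30)
- change from baseline: SD × √(2(1 − r)) × √(2/30)
- Week 24 with baseline as covariate: SD × √(1 − r²) × √(2/30)

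Relative to the unadjusted comparison, the ratio depends on r alone:

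| r | Change | Baseline as covariate |
|---|---|---|
| 0.90 | 0.447 | 0.436 |
| 0.95 | 0.316 | 0.312 |
| 0.97 | 0.245 | 0.243 |

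To turn this into power, assume SD 800 mL and a true difference of 150 mL. Neither is in the documents. At r = 0.95 the standard errors are 206.6, 65.3 and 64.5 mL. Two-sided power by the normal approximation:

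| r | Unadjusted | Change | Baseline as covariate |
|---|---|---|---|
| 0.90 | 0.11 | 0.37 | 0.38 |
| 0.95 | 0.11 | 0.63 | 0.64 |
| 0.97 | 0.11 | 0.84 | 0.85 |

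Varying the other two assumptions at r = 0.95: with SD 1000 mL and a difference of 100 mL, power is 0.07, 0.23 and 0.24. With SD 600 mL and a difference of 200 mL, it is 0.25, 0.98 and 0.99. The order of the three methods is the same throughout.

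For 6MWD the correlation may be lower. At r = 0.5 the ratios are 1.00 for change and 0.87 with baseline as covariate, so change then gains nothing while the covariate still helps.

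**The case against.** The best defence is that Table 1 and the visit list govern conduct and are clear, that the Aim 2 wording is an obvious leftover, and that the endpoint definitions already compare baseline with Week 24. On that reading an analyst would naturally use change, and most of the loss disappears. The endpoints are also secondary and admitted to be underpowered. Much of this stands, and it keeps the point small. It does not remove it: the endpoint wording describes a comparison over time and names no between-arm contrast, while Section 2.8.1 makes the last observed value the primary measure and gives baseline no role.

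Three stronger readings are tempting and are not supported:

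- *The planned model does not fit the data.* Step 3 shows that a two-point model is valid and equals the comparison of change.
- *The treatment effect would be diluted by averaging the arm effect over baseline and Week 24.* Section 2.8.1 states no such averaged term, and the endpoint definitions point away from it.
- *Sites would collect FVC at three extra visits, or 6MWD timing is also inconsistent.* Sites work from the visit list and Table 1, which show no interim spirometry, and every statement of 6MWD timing can be read as baseline and Week 24.

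**Conclusion.** The point holds in a limited form. The FVC timing in Aim 2 contradicts the rest of the current text, which by itself is close to clerical. The more useful part is that Section 2.8.1 leaves the between-arm analysis of FVC and 6MWD unstated and permits an unadjusted comparison of last values. For a measure with a baseline to Week 24 correlation of 0.90 to 0.97, that comparison has a standard error 2.3 to 4.1 times that of the baseline-adjusted one (1/0.436 to 1/0.243). The power figures rest on assumed SD, difference and correlation and serve as illustration only. Whether change or the covariate form is chosen matters little for FVC (0.63 against 0.64); what matters is that baseline is used and that the choice is fixed in advance. Severity is minor to moderate, since only secondary endpoints are affected.

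**What to change.** 1. Reword Aim 2 in Section 1.2 so that C1M is measured at baseline and at six-week intervals, and FVC and 6MWD at baseline and Week 24.
2. In Section 2.8.1, keep the trajectory, velocity and multi-visit repeated-measures wording for o,o'-dityrosine and C1M.
3. In the same section, state for FVC and for 6MWD a between-arm comparison of the Week 24 value with the baseline value as covariate. An arm-by-time model or a constrained-baseline model, in which baseline is itself an outcome, is also acceptable provided that one is named in advance.
4. When replacing the last-value rule for these two endpoints, say how a missing Week 24 value is handled, because the last observed value is then the baseline itself.

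The cost is a few sentences in two sections. No added visits, tests or patients are needed, and the baseline values are already collected.

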1.3 BACKGROUND INFORMATION

1.3.1 Idiopathic Pulmonary Fibrosis (IPF):

IPF is an enigmatic fibrotic lung disease that has an estimated annual incidence of 100,000 patients in the U.S. (1). Many other cases likely go undiagnosed, and the frequency of this disorder appears to be increasing (2,3). This morbid syndrome occurs almost exclusively in older adults. IPF is characterized by pathological accumulations of cross-linked lung extracellular matrix proteins (ECM) produced by fibroblasts, and their activated, differentiated progeny (e.g., myofibroblasts [myo-Fb]). The disease manifests with progressive, unremitting dyspnea and hypoxemia. Although two drugs were recently approved for treatment of IPF, the benefit of these agents appears to be mostly limited to slowing the progression of pulmonary restriction (4,5). IPF continues to have a median survival of 3-4 years after diagnosis, which is a worse prognosis than many common malignancies.

Given the impact and lethality of IPF, and only partial effectiveness of currently available therapeutics, there is an obvious and compelling need to develop new, more efficacious, mechanistically-based medical treatments for this disorder.

[figure not shown]
1.3.2 Oxidative Stress in IPF:

Although the etiology of IPF is unknown, several lines of evidence indicate oxidative stress plays an important role in the pathogenesis of this disease (6-8). Studies of lung tissue from IPF patients demonstrate “signatures” of chronic oxidative damage to the alveolar epithelium (9,10). The cellular/enzymatic sources of ROS in fibrotic lungs have traditionally been attributed to alveolar inflammatory cells (11-14). However, recent studies indicate that myofibroblasts (myo-

Fbs), key effector cells of fibrogenesis, also contribute to oxidative stress in fibrotic disorders (15-18). Recent studies have shown the pro-fibrotic cytokine transforming growth factor- β 1 (TGF- β 1) is a potent inducer of extracellular hydrogen peroxide (H_2O_2) production by human lung myo-Fbs (19-22). The enzymatic source of ROS production in myo-Fbs is a member of the NOX family of nicotinamide adenine dinucleotide phosphate-oxidase (NADPH) oxidases, specifically NOX4 (15,23,24).

1.3.3 NOX4 Mediates myo-Fb Activation:

The biochemical and functional characteristics of NOX4 are distinct in comparison to other NOX homologs in that extracellular generation of H_2O_2 (vs $O_2^{\cdot-}$) is a consistent and unique feature of the former (25-29). NOX4 has been identified as one of the most highly induced genes in a whole-genome Affymetrix analysis of human lung fibroblasts stimulated with TGF- β 1; other members of the NOX gene family were not affected at the mRNA level (**Fig. 1**). These data implicate NOX4 as the primary enzymatic source of TGF- β 1-induced extracellular H_2O_2 generation by differentiated myofibroblasts. Importantly, NOX1 was not identified in these cells or in human IPF myo-Fbs.

[figure not shown]

Pharmacologic or RNAi-mediated inhibition of NOX4 expression/activity has been shown to significantly inhibit TGF- β 1-induced myo-Fb H_2O_2 production, ECM synthesis, and contractility (15). Together, these studies indicate a critical role for NOX4-dependent H_2O_2 in conferring synthetic and contractile properties to myo-Fbs that differentiate under the influence of TGF- β 1.

1.3.4 NOX4 is Expressed in Bleomycin-Induced Lung Injury:

The role of NOX4 in injury-induced fibrosis has been studied in a murine model of lung injury. Intra-tracheal instillation of bleomycin induces epithelium injury in mice that leads to fibrosis, which peaks 2-3 weeks post-injury (15,30). NOX4 expression was induced in a time-dependent manner after the induction of lung injury, increasing from day 7 up to day 28 (**Fig. 2**), supporting a temporal relationship between NOX4, myo-Fbs activation, and fibrosis. In contrast, expression of the NOX2 isoform, which is predominantly expressed in phagocytic cells, was increased on day 7 and returned to baseline levels at later time-points when inflammatory responses have subsided (**Fig. 2**).

[figure not shown]
Figure 2: Expression of NOX4 and NOX2 in the lung following bleomycin-induced lung fibrosis.

1.3.5 Myo-Fb-Generated H₂O₂ Mediates o,o'-dityrosine-Dependent ECM Crosslinking:

The ECM overlying TGF-β1-stimulated Fbs has been previously shown to be susceptible to crosslinking reactions on L-tyrosine residues (21). A Genbank database search of the number and % tyrosine residues in 11 different ECM proteins was performed to identify endogenous targets for these residues. Of these candidate proteins, fibronectin demonstrated the highest number and % tyrosines (90 total residues; 3.84% of all amino acids). We tested to see if fibronectin co-localizes with the crosslinking reactions of tyramide FITC with endogenous tyrosine residues on the ECM proteins (**Fig. 3**); this demonstrated that fibronectin immunoreactivity is closely associated with the tyramide-FITC signal, which suggests that tyrosine residues on fibronectin may be susceptible to phenol:phenol (tyrosine:tyramide-FITC) crosslinking. This tyramide-FITC labeling reaction is present only in TGF-β1-treated cells in the presence of heme peroxidase, horseradish peroxidase (HRP), is abolished by diphenyleneiodonium (DPI) co-treatment and is markedly reduced by catalase. These findings support the requirement for heme peroxidase-catalyzed, oxidative crosslinking of ECM-associated fibronectin. However, the turnover of oxidatively modified ECM proteins in the lung and their potential release into the circulation has not been well characterized.

Figure 3: Fibronectin co-localizes with H₂O₂-dependent, peroxidase-catalyzed crosslinking reactions. Fbs were stimulated with TGF-β (2 ng/ml) for 16 h to generate myo-Fbs that generate extracellular H₂O₂; they were then incubated with horseradish peroxidase (HRP), and the tyrosine analog, tyramide-FITC, for a period of 1h at 37°C. Cells were then fixed and stained with a monoclonal antibody to fibronectin and a TRITC-conjugated secondary antibody (left panel). The FITC-generated signal co-localizes with the fibronectin-TRITC label only under conditions of H₂O₂ generation and peroxidative activity.

1.3.6 Evidence of *o,o'*-dityrosine Formation in IPF Fibroblast Foci:

In-vitro data in TGF- β 1-stimulated myo-Fbs suggests that heme peroxidase may catalyze dityrosine-dependent protein crosslinking (**Fig 3**). Immunohistochemical (IHC) staining of IPF lung tissue using a monoclonal antibody to *o,o'*-dityrosine shows this moiety is specifically expressed in fibroblastic foci, a hallmark lesion of IPF (**Fig. 4**).

[figure not shown]

Figure 4: Fibroblastic foci in UIP/IPF demonstrate expression of dityrosine, a marker of oxidative protein cross-linking reactions. IPF tissue sections were stained with a mouse monoclonal antibody (1:50 dilution) against dityrosine by immunohistochemistry (TruBlue). Control staining was with biotinylated secondary IgG antibody. Intense staining of dityrosine was identified primarily in fibroblastic foci around alveolar spaces (AS). Arrows point to dityrosine-expressing (blue staining) fibroblastic foci in UIP/IPF.

These findings have been interpreted as evidence the myo-Fbs within these foci actively secrete H_2O_2 , which then induces the formation of oxidatively- modified proteins by a *o,o'*-dityrosine-dependent mechanism.

1.3.7 Plasma levels of *o,o'*-dityrosine Are Increased in IPF Patients:

Tyrosine residues in proteins are susceptible to covalent oxidative modifications, including the formation of *o,o'*-dityrosine (31) (**Fig. 5**). Since these covalent modifications are stable, protein tyrosine (P-Tyr) modifications in circulating plasma may serve as a potential biomarker of oxidative injury.

[figure not shown]
[figure not shown]

Figure 5: Chemical structure and extracted ion chromatograms measures of soluble *o,o'*-dityrosine. (A) Chemical structure of *o,o'*-dityrosine. 'R' represents the α -carbon linking the peptide bonds within a protein molecule. (B) Chromatogram from plasma of a subject with IPF. The protein hydrolysate from plasma samples were separated by reverse phase HPLC and subjected to ESI/MS. Extracted ion chromatograms were derived from the MRM transitions for *o,o'*-dityrosine. The ratio of ion currents for each amino acid compared with the internal standard (depicted by *) was utilized to quantify the levels of *o,o'*-dityrosine; note co-elution of authentic oxidized amino acid to the corresponding isotopically labeled internal standard.

We found plasma concentrations of *o,o'*-dityrosine were much greater among IPF patients (8.51 ± 0.94 $\mu\text{mol/mole}$ tyrosine) compared to healthy controls (0.47 ± 0.07 $\mu\text{mol/mole}$ tyrosine) (**Fig. 6**). The respective values for individuals within these two groups were almost completely separated and, overall, there was an 18-fold intergroup difference.

Figure 6: *o,o'*-dityrosine is increased in plasma of IPF patients.

Plasma from IPF and healthy control subjects were analyzed by mass spectrometry for *o,o'*-Dityrosine, $n=42$ healthy control subjects, $n=32$ IPF subjects; values represent mean \pm SEM.

1.3.8. The NOX1/4 Inhibitor GKT137831 Reverses Established Fibrosis:

Aged mice (18 months old) have impaired capacity for fibrosis resolution after bleomycin injury compared to young mice (2 months) (32). This model was used to test whether delayed administration of GKT137831 in aged mice results in reversal of the persistent fibrosis. The GKT137831-treated mice exhibited decreased myo-Fb accumulation (**Fig. 7A**). Recovery to baseline weights was also observed in these animals, whereas vehicle-treated (control) mice remained below baseline levels throughout the 6-week observation period (**Fig. 7B**). Most importantly, GKT137831 treatment led to a reversal of age-associated persistent fibrosis (**Figs. 7A and 7C**), and a reduction in mortality (**Fig. 7D**). These data suggest that GKT137831 treatment in a model of persistent fibrosis leads to modulation of myo-Fb phenotype/fate that bespeaks for the potential reversibility of established lung fibrosis.

[figure not shown]

Figure 7: *In vivo* pharmacological targeting of NOX4 with GKT137831 leads to reversal of age-associated persistent fibrosis. (A to D) Aged mice (18 months old) were subjected to bleomycin-induced lung fibrosis. Mice were treated daily with GKT137831 (40 mg/kg) or vehicle by oral gavage starting at 3 weeks after injury, through week 6 (21 treatments total). Body weight of the mice was recorded weekly (**B**). Values represent means \pm SEM; $n = 17$ to 21 per group; * $p < 0.05$ (**A and C**) Lung tissues were harvested from

control (uninjured) mice or mice at 6 weeks after injury. Tissues were evaluated by Masson's trichrome blue staining for collagen and by IHC analyses to evaluate expression of α -SMA. Whole-lung homogenates were analyzed by quantitative hydroxyproline assay (C). Data are expressed as total micrograms of hydroxyproline per whole lung. Values represent means \pm SEM; n = 9 to 10 per group; *p < 0.05. Kaplan-Meier survival curve for GKT137831-treated (n = 22) and vehicle-treated (n = 23) mice (D). P < 0.05, log-rank test. Scale bars, 100 mm.

1.3.9. GKT137831 Reduces Plasma Levels of o,o'-dityrosine Mice with Lung Injury:

The effects of GKT137831 on plasma levels of ROS-associated biomarkers was tested in mice with and without bleomycin-induced lung injury. Bleomycin treatment again resulted in a striking increase in plasma levels of o,o'-dityrosine (Figure 8), analogous to findings in humans with IPF (see Section 1.3.7). Most importantly, GKT137831 therapy resulted in >5-fold reductions of plasma o,o'-dityrosine among the bleomycin-treated animals with pulmonary fibrosis. This GKT137831 treatment effect on o,o'-dityrosine was of a greater magnitude and more significant than reductions of other ROS biomarkers (3'-nitrotyrosine and 3'-chlorotyrosine) (data not shown).

[figure not shown]

Figure 8. GKT831 administration causes *in vivo* reductions of mechanistic ROS biomarker o,o'-dityrosine. Aged female B6 mice were treated with intra-tracheal bleomycin or saline, and then GKT831 (40 mg/kg) was administered daily by gavage. While bleomycin treatment resulted in large increases in circulating o,o'-dityrosine, levels of this metabolite were normalized by GKT831 therapy. N=6 in GKT831-treated groups, # denotes p = 0.012).

